10.2 Sample Size and Expected Accrual

The total sample size will be 70 patients Patient accrual is projected to be approximately 3 patients per month. Thus accrual is likely to proceed for 8 to 24 months.

11.0LABELING, PACKAGING, STORAGE AND RETURN OF CLINICAL SUPPLIES

11.1 Investigational Product

The investigator shall take responsibility for and shall take all steps to maintain appropriate records and ensure appropriate supply, storage, handling, distribution and usage of investigational product in accordance with the protocol and any applicable laws and regulations.

Clinical Supplies will be provided by Merck as summarized in Table 7.

Table 7 Product Descriptions

Product Name & Potency	Dosage Form	
Pembrolizumab 50 mg	Lyophilized Powder for Injection	
Pembrolizumab 100 mg/ 4mL	Solution for Injection	

11.2 Packaging and Labeling Information

Clinical supplies will be affixed with a clinical label in accordance with regulatory requirements.

11.3 Clinical Supplies Disclosure

This trial is open-label; therefore, the subject, the trial site personnel, the Sponsor and/or designee are not blinded to treatment. Drug identity (name, strength) is included in the label text; random code/disclosure envelopes or lists are not provided.

11.4 Storage and Handling Requirements

Clinical supplies must be stored in a secure, limited-access location under the storage conditions specified on the label.

Receipt and dispensing of trial medication must be recorded by an authorized person at the trial site.

Clinical supplies may not be used for any purpose other than that stated in the protocol.

11.5 Returns and Reconciliation

The investigator is responsible for keeping accurate records of the clinical supplies received from Merck or designee, the amount dispensed to and returned by the subjects and the amount remaining at the conclusion of the trial.

Upon completion or termination of the study, all unused and/or partially used investigational product will be destroyed at the site per institutional policy. It is the Investigator's responsibility to arrange for disposal of all empty containers, provided that procedures for proper disposal have been established according to applicable federal, state, local and institutional guidelines and procedures, and provided that appropriate records of disposal are kept.

12.0 ADMINISTRATIVE AND REGULATORY DETAILS

12.1 Institutional Review Board (IRB) Approval and Consent

Unless otherwise specified, each participating institution must obtain its own IRB approval. It is expected that the IRB will have the proper representation and function in accordance with federally mandated regulations. The IRB should approve the consent form and protocol.

In obtaining and documenting informed consent, the investigator should comply with the applicable regulatory requirement(s), and should adhere to Good Clinical Practice (GCP) and to ethical principles that have their origin in the Declaration of Helsinki.

Before recruitment and enrollment onto this study, the patient will be given a full explanation of the study and will be given the opportunity to review the consent form. Each consent form must include all the relevant elements currently required by the FDA Regulations and local or state regulations. Once this essential information has been provided to the patient and the investigator is assured that the patient understands the implications of participating in the study, the patient will be asked to give consent to participate in the study by signing an IRB approved consent form.

Prior to a patient's participation in the trial, the written informed consent form should be signed and personally dated by the patient and by the person who conducted the informed consent discussion.

12.2 Food and Drug Administration (FDA) Approval

This study will be conducted under an IND held by [name] at the University of Chicago. The University of Chicago CCTO will be responsible for facilitating all communications with the FDA on behalf of the IND holder. Participating sites should not communicate directly with the FDA.

12.3 Required Documentation

Prior to the selection of a study site that is not a full member of the Personalized Cancer Care Consortium, the audit and trial oversight processes for the site must be reviewed and approved by the UC CCC Clinical Research Advisory Committee.

Before the study can be initiated at any site, the following documentation must be provided to the Cancer Clinical Trials Office (CCTO) at the University of Chicago Comprehensive Cancer Center.

- A copy of the official IRB approval letter for the protocol and informed consent
- IRB membership list
- CVs and medical licensure for the principal investigator and any sub-investigators who will be involved in the study.
- Form FDA 1572 appropriately filled out and signed with appropriate documentation
- CAP and CLIA Laboratory certification numbers and institution lab normal values
- Investigational drug accountability standard operating procedures

Additionally, before the study can be initiated at any site, the required executed research contract/subcontract must be on file with the University of Chicago.

12.4 Data and Safety Monitoring

This study will be remotely monitored by the designated University of Chicago Clinical Research Associate (CRA) in accordance with the University of Chicago, Section of Hematology/Oncology standard operating procedure titled Monitoring of Multi-Institutional Investigator Initiated Clinical Trials.

Prior to subject recruitment, and unless otherwise specified, a participating site will undergo a Site Initiation Teleconference to be conducted by the designated University of Chicago research team. The site's principal investigator and his or her study staff must attend the site initiation meeting.

Monitoring will be conducted to verify the following:

- Adherence to the protocol
- Completeness and accuracy of study data and samples collected
- Compliance with regulations
- Submission of required source documents

Participating sites will also undergo a site close-out teleconference upon completion, termination or cancellation of a study to ensure fulfillment of study obligations during the conduct of the study, and to ensure that the site Investigator is aware of his/her ongoing responsibilities.

Unless otherwise specified, this protocol will undergo weekly review at the multi-institutional data and safety monitoring teleconference as per procedures specified by the UC CCC NCI-approved Data and Safety Monitoring Plan. The conference will review:

- Enrollment rate relative to expectations, characteristics of participants
- Safety of study participants (Serious Adverse Event & Adverse Event reporting)
- Adherence to protocol (protocol deviations)
- Completeness, validity and integrity of study data
- Retention of study participants

Protocol deviations are to be documented using the Protocol Deviation Form and sent via email to [contact]. Deviations that are considered major because they impact subject safety or alter the risk/benefit ratio, compromise the integrity of the study data, and/or affect subjects' willingness to participate in the study must be reported within 7 days. Please contact the University of Chicago CRA ([contact]) if you have questions about how to report deviations. All major protocol deviations should also be reported to the local IRB of record according to their policies and procedures.

12.5 Auditing

In addition to the clinical monitoring procedures, the University of Chicago Comprehensive Cancer Center will perform routine Quality Assurance Audits of investigator-initiated clinical trials as described in the NCI-approved UC CCC DSM Plan. Audits provide assurance that trials are conducted and study data are collected, documented and reported in compliance with the protocol. Further, quality assurance audits ensure that study data are collected, documented and reported in compliance with Good Clinical Practices (GCP) Guidelines and regulatory requirements. The audit will review subjects enrolled at the University of Chicago in accordance with audit procedures specified in the UC CCC Data and Safety Monitoring plan.

For institutions who are formal members of the Personalized Cancer Care Consortium (PCCC), the UC CCC will conduct on site quality assurance audits on average every two years during the enrollment and treatment phase of the study.

Auditing procedures for participating sites that are not full members of the PCCC must be specified and approved by the UC CCC Clinical Research Advisory Committee. In general, for sites that are not full members of the PCCC, auditing responsibility will be delegated to the participating center, with the annual audit report forwarded to the University of Chicago for review.

A regulatory authority (e.g. FDA) may also wish to conduct an inspection of the study, during its conduct or even after its completion. If an inspection has been requested by a regulatory authority, the site investigator must immediately inform the University of Chicago Cancer Clinical Trials Office and Regulatory Manager that such a request has been made.

12.6 Amendments to the Protocol

All modifications to the protocol, consent form, and/or questionnaires will be submitted to the University of Chicago IRB for review and approval. A list of the proposed modifications or amendments to the protocol and/or an explanation of the need of these modifications will be submitted, along with a revised protocol incorporating the modifications. Only the Study Lead PI can authorize any modifications, amendments, or termination of the protocol. Once a protocol amendment has been approved by the University of Chicago IRB, the Regulatory Manager will send the amended protocol and consent form (if applicable) to the affiliate institutions electronically. Upon receipt of the packet the affiliate institution is expected to do the following:

- The affiliate must reply to the email from the Regulatory Manager indicating that the amendment was received by the institution and that it will be submitted to the local IRB.
- The amendment should be submitted to the affiliate institution's IRB as soon as possible after receipt. The amendment **must** be IRB approved by the institution **within 3 months** from the date that it was received.
- The University of Chicago version date and/or amendment number must appear on the affiliate consent form and on the affiliate IRB approval letter. The version dates can be found on the footer of every page of the protocol and consent form. The amendment number can be found on the University of Chicago IRB amendment approval letter that is sent with the protocol/amendment mailing.

The IRB approval for the amendment and the amended consent form (if amended consent is necessary) for the affiliate institution must be sent to the designated UC Regulatory Manager as soon as it is received

12.7 Annual IRB Renewals, Continuing Review and Final Reports

A continuing review of the protocol will be completed by the University of Chicago IRB and the participating institutions' IRBs at least once a year for the duration of the study. The annual IRB renewal approvals for participating institutions should be forwarded promptly to the Regulatory Manager. If the institution's IRB requires a new version of the consent form with the annual renewal, the consent form should be included with the renewal letter.

12.8 Record Retention

Study documentation includes all CRFs, data correction forms or queries, source documents, Sponsor-Investigator correspondence, monitoring logs/letters, and regulatory documents (e.g., protocol and amendments, IRB correspondence and approval, signed patient consent forms).

Source documents include all recordings of observations or notations of clinical activities and all reports and records necessary for the evaluation and reconstruction of the clinical research study.

Government agency regulations and directives require that all study documentation pertaining to the conduct of a clinical trial must be retained by the study investigator. In the case of a study with a drug seeking regulatory approval and marketing, these documents shall be retained for at least two years after the last approval of marketing application in an International Conference on Harmonization (ICH) region. In all other cases, study documents should be kept on file until three years after the completion and final study report of this investigational study.

12.9 Obligations of Study Site Investigators

The Study Site Principal Investigator is responsible for the conduct of the clinical trial at the site in accordance with Title 21 of the Code of Federal Regulations and/or the Declaration of Helsinki. The Study Site Principal Investigator is responsible for personally overseeing the treatment of all study patients. He/she must assure that all study site personnel, including sub-investigators and other study staff members, adhere to the study protocol and all FDA/GCP/NCI regulations and guidelines regarding clinical trials both during and after study completion.

The Study Site Principal Investigator at each institution or site will be responsible for assuring that all the required data will be collected and entered into the CRFs. Periodically, monitoring visits or audits will be conducted and he/she must provide access to original records to permit verification of proper entry of data.

53

13.0 APPENDICES

13.1 ECOG Performance Status

Grade	Description	
0	Normal activity. Fully active, able to carry on all pre-disease	
	performance without restriction.	
	Symptoms, but ambulatory. Restricted in physically strenuous	
1	activity, but ambulatory and able to carry out work of a light or	
	sedentary nature (e.g., light housework, office work).	
	In bed <50% of the time. Ambulatory and capable of all self-care, but	
2	unable to carry out any work activities. Up and about more than 50%	
	of waking hours.	
3	In bed >50% of the time. Capable of only limited self-care, confined	
)	to bed or chair more than 50% of waking hours.	
4	100% bedridden. Completely disabled. Cannot carry on any self-care.	
4	Totally confined to bed or chair.	
5	Dead.	

^{*} As published in Am. J. Clin. Oncol.: Oken, M.M., Creech, R.H., Tormey, D.C., Horton, J., Davis, T.E., McFadden, E.T., Carbone, P.P.: Toxicity And Response Criteria Of The Eastern Cooperative Oncology Group. Am J Clin Oncol 5:649-655, 1982. The Eastern Cooperative Oncology Group, Robert Comis M.D., Group Chair.

13.2 Common Terminology Criteria for Adverse Events V4.0 (CTCAE)

The descriptions and grading scales found in the revised NCI Common Terminology Criteria for Adverse Events (CTCAE) version 4.0 will be utilized for adverse event reporting. (http://ctep.cancer.gov/reporting/ctc.html)

13.3 Evaluation of Tumor Response by immune-related Response Evaluation Criteria in Solid Tumors (irRECIST)

Tumor response will be assessed by the irRECIST (Nishino et al, 2013)²⁴. This standard is a reconciliation of RECIST guidelines v1.1 with the original immune-related Response Criteria (irRC) (Wolchok et al, 2009)²⁵. The latter standard incorporated principles important for assessment of immune-checkpoint blocking immunotherapy for cancer, but fundamentally differed from RECIST in using 2-dimensional tumor assessment. In contrast, irRECIST is based on 1-dimensional tumor measurement, but it differs from RECIST guidelines v1.1 in the following key ways:

• Under RECIST guidelines v1.1, the appearance of new lesions indicates PD. Under irRECIST, new measurable lesions are incorporated in the tumor burden, which is used to determine immune-related progressive disease (irPD), immune-related partial

response (irPR), and immune-related complete response (irCR). New non-measurable lesions preclude irCR.

• Under RECIST guidelines v1.1, there is no confirmation for PD. In addition, responses and irPDs must be confirmed by consecutive scans at least 4 weeks apart, assuming no clinical deterioration.

The following sub-sections describe irRECIST in detail.

Tumor Burden

At baseline, the tumor burden is the sum of single diameters (short axis for nodal lesions, longest diameter for other lesions) for the target lesions. In subsequent scans, the diameters of new measurable lesions are added to the tumor burden. If a subject is retreated, then up to 5 target lesions (perhaps different from the original lesions) will be selected and a new baseline tumor burden will be established.

Overall Response at a Single Time Point

The table below outlines determination of disease response at a single assessment based on irRECIST.

irRECIST: Overall Response

Tumor Burden (Baseline and New)	Non-Target Lesions (Baseline and New)	Response
Disappearance of non-nodal lesions. All pathologic lymph nodes < 10 mm (short axis)	Disappearance of non-nodal lesions. All pathologic lymph nodes < 10 mm (short axis)	irCR ^a
≥ 30% decrease from baseline	Any	irPR ^a
≥ 20% increase from nadir and at least 5 mm	Any	irPD ^a
Neither sufficient decrease to qualify for PR, nor sufficient increase to qualify for PD	Any	irSD
Disappearance of all non-nodal lesions. All pathologic lymph nodes < 10 mm	Any other than disappearance of all non- nodal lesions and reduction of pathologic lymph nodes < 10 mm	irPRª
Not all evaluated ^b	Any	irNE

a Selection as best response requires confirmation by 2 consecutive measurments at least 4 weeks apart.

b If some lesions are measured, response may be inferred from available measurements. For example, growth in evaluated target lesions may be sufficient for irPD regardless of status of non-evaluated lesions.

Product: PEMBROLIZUMAB 56

Protocol/Amendment No.:

REFERENCES

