4.2.3.1 Efficacy Endpoints

The primary efficacy objective of this trial is to evaluate the anti-tumor activity of the combination of pembrolizumab and ipilimumab in subjects with advanced melanoma who

have previously been treated with an anti-PD1/L1 antibody. Response rates per irRECIST will be evaluated.

irRECIST as assessed by the investigator will be used as the primary response rate efficacy endpoint. irRECIST will also be used by the local site to determine eligibility and make treatment decisions. The primary efficacy endpoint is response rate based on irRECIST. Secondary endpoints are listed in section 3.2.

Immunotherapeutic agents such as pembrolizumab may produce antitumor effects by potentiating endogenous cancer-specific immune responses which may be functionally anergic. The response patterns seen with such an approach may extend beyond the typical time course of responses seen with cytotoxic agents, and can manifest a clinical response after an initial increase in tumor burden or even the appearance of new lesions. Standard RECIST criteria may not provide a complete response assessment of immunotherapeutic agents such as pembrolizumab therefore the irRECIST have been developed to encompass this.

Broadly, irRECIST includes the concept of treatment beyond progression, if radiologic imaging shows PD, tumor assessment should be repeated ≥ 4 weeks later in order to confirm PD with the option of continuing treatment per below while awaiting radiologic confirmation of progression. If repeat imaging shows a reduction in the tumor burden compared to the initial scan demonstrating PD, treatment may be continued as per treatment calendar. If repeat imaging confirms progressive disease, subjects will be discontinued from trial therapy. In determining whether or not the tumor burden has increased or decreased, Investigators should consider all target lesions as well as non-target lesions.

In subjects who have initial evidence of radiological PD, it is at the discretion of the treating physician whether to continue a subject on study treatment until repeat imaging is obtained a minimum of 4 weeks later. This decision should be based on the clinical judgment of the subject's overall clinical condition, including performance status, clinical symptoms, and laboratory data. Subjects may receive treatment while waiting for confirmation of PD if they are clinically stable as defined by the following criteria:

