10.1 Statistical Analysis Plan

The primary endpoint of the study will be response rate by irRECIST criteria. A Simon (Cont Clin Trials, 1980), optimal two-stage design will be employed to test the null hypothesis of a 10% response rate (based on historical ipilimumab alone) vs. a 30% alternative. Twelve

patients will be entered into the first stage and if 1 or fewer responses are observed then the trial will be terminated for lack of activity. Otherwise an additional 23 patients will be enrolled for a total of 35. If 5 or fewer responses are observed the treatment will be considered insufficiently active whereas if 6 or more (>17%) are seen the null hypothesis will be rejected and the treatment considered worthy of further testing. This design has an alpha level of 0.10 (1-sided), 90% power, and a 0.65 probability of stopping early if the true response rate is only 10%. With the closing of cohort 2, we will enroll an additional 35 patients who had initial progression if 6 or more patients respond among the initial 35. This will bring the total sample size to n=70, and provide additional precision for the estimated response rate and other secondary endpoints. For response rate, assuming a true rate of 30%, n=70 subjects will provide a 90% confidence interval width of $\pm 9.0\%$.

Evaluable patients will be defined as any eligible patient who receives a dose of pembrolizumab in combination with ipilimumab.

Secondary endpoints will include estimation of progression-free survival using the Kaplan-Meier method and assessment of changes in biomarkers from pre-post treatment using paired t-tests or Wilcoxon signed-rank tests.

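### The irPR rule ignores non-target growth and new non-measurable lesions, tumor burden has two meanings, and footnote b does not confine inference from partly measured disease to irPD

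*Combined protocol and SAP*

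**What the plan says.** Section 10.1 sets the endpoint: "The primary endpoint of the study will be response rate by irRECIST criteria". Section 4.2.3.1 names the assessor: "irRECIST as assessed by the investigator will be used as the primary response rate efficacy endpoint". The same section also uses irRECIST for treatment decisions.

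Section 13.3 supplies the rules:

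- **Tumor burden.** "At baseline, the tumor burden is the sum of single diameters" of the target lesions. Diameters of new measurable lesions are added at later scans. Non-target lesions are not part of it.
- **irPR.** The tumor-burden column requires "≥ 30% decrease from baseline". The non-target column, which covers baseline and new lesions, reads *Any*. A further row gives irPR when target disease has disappeared but non-target disease has not, whatever else the latter is doing.
- **irPD.** The tumor-burden column requires "≥ 20% increase from nadir and at least 5 mm", again with *Any* for non-target lesions. The irSD row also reads *Any*.
- **New non-measurable lesions.** "New non-measurable lesions preclude irCR". Nothing is said about irPR.
- **Confirmation.** Under footnote a, irCR, irPR and irPD count as best response only if confirmed at least 4 weeks apart.
- **Incomplete assessment.** The default is irNE, but footnote b adds: "If some lesions are measured, response may be inferred from available measurements". Its single example is irPD.

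Section 4.2.3.1, at the end of a paragraph on repeat imaging after a first PD, says that in judging whether tumor burden has risen or fallen, "Investigators should consider all target lesions as well as non-target lesions".

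**The concern.** Three features of the text can each move a patient into the responder count.

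First, a patient whose target lesions shrink by 30%, with confirmation, is a responder even if non-target disease is clearly growing or new non-measurable lesions have appeared.

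Second, tumor burden is a measured sum in section 13.3 and something wider in section 4.2.3.1. An investigator who has both passages open can reach different conclusions from one scan, depending on whether the question is treatment or endpoint.

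Third, footnote b is worded for response in general. Inference from incomplete measurement is safe for irPD, because growth already seen in the measured lesions can be enough. It is not safe for irPR: a follow-up sum that lacks a lesion, set against a full baseline sum, looks like shrinkage.

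The first and third act mainly towards more responders. The responder count decides whether the trial stops at 12 patients, whether the null is rejected at 35, and whether a further 35 patients are enrolled.

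**Working it through.** **Step 1. The table read row by row.** Take a patient with a confirmed 30% fall in tumor burden, growing non-target disease and no new measurable lesion. The irPR row is met, because its non-target entry is *Any*. The irPD row is not met unless the measured sum has risen enough from nadir. Replace the non-target growth by new non-measurable lesions and the result is the same: irCR is excluded, irPR is not. Later regrowth of target lesions, or new measurable lesions, can still produce irPD.

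**Step 2. Sections 13.3 and 4.2.3.1 side by side.** In 13.3 the burden is target plus new measurable lesions. In 4.2.3.1 non-target lesions enter the judgment as well. On a repeat scan where the measured sum meets the irPR row while non-target disease has grown, the first gives irPR and the second can be read as continued progression.

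**Step 3. Footnote b (invented example).** Baseline targets are 50 mm and 30 mm, sum 80 mm. At follow-up the second is not measured and the first is 55 mm.

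- Available sum against full baseline: (55 − 80)/80 = −31%, past the irPR threshold.
- Measured lesion against its own baseline: (55 − 50)/50 = +10%.

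Footnote b neither requires the same lesions on both sides of the comparison nor endorses this calculation.

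**Step 4. The plan's own design figures.** Inputs from section 10.1: n1 = 12, stop at 1 or fewer responses; n = 35, reject at 6 or more; null 10%, alternative 30%. With X1 ~ Bin(12, p) and X2 ~ Bin(23, p):

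- P(stop early) = (1 − p)^12 + 12p(1 − p)^11
- P(reject) = Σ over x = 2 to 12 of P(X1 = x) × P(X2 ≥ 6 − x)

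At p = 0.10, P(stop early) = 0.2824 + 0.3766 = 0.659 (stated 0.65). P(reject) = 0.0977 (stated alpha 0.10). At p = 0.30, P(reject) = 0.9014 (stated 90%). The design figures reproduce, so there is no arithmetic error in the plan.

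**Step 5. Illustration of sensitivity.** Let f be the share of true non-responders labelled irPR through these rules. The documents give no value; 1%, 3% and 5% are assumptions. At a true rate of 10% the apparent rate is 0.10 + 0.90f.

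| f | Apparent rate | P(reject null) | P(stop at 12) | False share of labelled responders |
|---|---|---|---|---|
| 0 | 0.100 | 0.098 | 0.659 | 0 |
| 1% | 0.109 | 0.132 | 0.618 | 0.9/10.9 = 8% |
| 3% | 0.127 | 0.214 | 0.538 | 2.7/12.7 = 21% |
| 5% | 0.145 | 0.309 | 0.463 | 4.5/14.5 = 31% |

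**The case against.** The best defense is that the table is clear and may be deliberate. The primary objective refers the reader to section 13.3 for irRECIST. Barring irCR, and only irCR, when new non-measurable lesions appear looks like a choice. The sentence in 4.2.3.1 concerns confirming PD and continuing treatment, not awarding irPR. This stands: a reader might infer that the plan holds two competing irPR rules, and the documents do not show that. What remains is one term with two meanings, in a section that uses irRECIST for both the endpoint and treatment decisions.

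The safeguards also count. Confirmation at least 4 weeks apart means that a lesion missed once would not by itself make a responder, and new measurable lesions do enter the sum. Neither looks at non-target growth or new non-measurable lesions.

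On footnote b, irNE is the default, the only example is irPD, and the response column covers every category, so inferring a response need not mean an objective response. It is fair to call this an ambiguity and not a permission. One sentence closes it.

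The planned PFS by RECIST v1.1, under which section 13.3 says new lesions are PD, would reveal some of the discordance. It would not show the effect on ORR.

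Finally, only non-responders with confirmed apparent shrinkage of at least 30% can be affected, and the last column of the table shows how large a false share the higher assumed rates imply. Nothing in the documents supports such shares, so those rates are not estimates.

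**Conclusion.** The point holds as a matter of definition. Followed as written, section 13.3 can count patients with growing non-target disease or new non-measurable lesions as responders, the meaning of tumor burden differs between two sections, and footnote b is open on irPR and irCR. The likely direction is upward.

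The size is unknown. The design has little slack: its exact alpha of 0.0977 is already close to the nominal 0.10, and an assumed 1% mislabelling takes the rejection probability to 0.132. That shows sensitivity and does not estimate the bias.

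Two further inferences should not be drawn. A reader might conclude that such patients can never become irPD; target regrowth or new measurable lesions can still make them so. A reader might also conclude that the historical 10% was measured by stricter criteria; the documents do not state which response criteria lie behind it.

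Whether non-target progression ought to block irPR in the primary analysis is debatable, and the point does not depend on it. The case for change rests on clarity and on making the effect visible at low cost.

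**What to change.** 1. Reconcile sections 4.2.3.1 and 13.3 so that one definition of tumor burden applies.
2. Limit footnote b to irPD. For irPR and irCR, require every target lesion to be measured; otherwise record irNE.
3. Keep the table's irPR rule for the primary analysis. At each irPR, record non-target status and any new non-measurable lesion.
4. Add to section 10.1 one sensitivity ORR in which irPR with unequivocal non-target progression, or with new non-measurable lesions, counts as non-response. Section 13.3 does not define unequivocal non-target progression, so a definition has to be written first.

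The cost is wording in the appendix and section 10.1, one data field and one table. No extra scans or readers are needed. The reported ORR may be slightly lower under item 2 and in the sensitivity analysis.
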